6.1 Eligibility Criteria

Inclusion Criteria:

- Clinician confirmed diagnosis of SSc-spectrum disorder.
- Eighteen years of age or older at the time of recruitment.
- Able to give full informed consent.
- Steady dose (for at least two weeks) of relevant prescribed drug (e.g., vasodilatory and vasoactive) therapies for SSc-associated vasculopathy.

Exclusion Criteria:

- Patients receiving treatment with intravenous vasodilatory/vasoactive therapy (e.g., iloprost)
- Finger DUs currently requiring hospital admission (e.g., to receive iloprost) or awaiting surgery for digital vasculopathy.
- Currently receiving phototherapy for clinical reasons (e.g., ultraviolet-B therapy).

•

We will use a purposeful sampling to recruit patients with representative spectrum of SSc:

- Disease duration: 'early' (<5 years) and 'late' (>5 years).
- Limited vs. diffuse cutaneous disease/subsets.
- Severity of digital (finger) skin sclerosis (i.e., sclerodactyly) although it is likely that many patients will have mild to moderate digital fibrosis.

6.2 Recruitment and Consent Procedure / Data collection procedure

Potential patients will be recruited from the specialist SSc clinic at Salford Royal Hospital. Primarily they will be identified as potential participants during the outpatient encounter. However they may also be identified through review of the patient electronic records and clinic lists by a member of the direct care team. They may also be approached during inpatient admissions at Salford Royal Hospital.

Potential patients will be given the patient information sheet and consent form. They will be given as much time as they require to read the documentation and to ask questions. Consent may be taken therefore when first approached. If they require further time to consider (e.g. beyond the day they attended the outpatient department), then they will be provided with the telephone numbers and email addresses of members of the direct care team to allow them the opportunity to ask any questions they may have. This will be followed up by a telephone call from one of the direct care team to ascertain whether or not they would be interested in taking part. This would be at least 24 hours after they received the study information (including patient information sheet and consent form) to allow time to consider their decision.

Members of the direct care team will also write to patients with a history of digital ulceration to offer them the opportunity to participate. This will include a covering patient invitation letter and the study patient information sheet. This will include the contact details of how to contact the research team if they wish to participate and/or have any queries. This will be followed up with a phone call (no less than 7 days after being sent) to follow up if they have not contacted the research team within this time period.

Informed consent will be taken by either a member of the direct care team or the research team. These will include the following individuals: [name], [name], [name], [name] and [name], all of whom have substantive or honorary contracts with Northern Care Alliance NHS Foundation Trust (NCA) and up to date GCP training.

6.3 Equality

The NHS Constitution states that access to research should be available to all; however the evidence indicates that participation in health research does not reflect the demography of the local or national population. This may have an impact on the validity and reliability of research findings when applied to the general population. Improving equality and access to research is one of the Sponsor's organisational priorities..

6.4 Study Duration

The study will recruit for a I year period with a proposed start date of 14/02/2025 with a recruitment end date of 13/02/2026 and a study end date (last patient, last visit) of 20/02/2026. Patients will attend a total of 3 study (morning) visits over 3 (ideally consecutive) days. The minimum time between study visits is 1 day, and the maximum time between study visits shall be 3 days. The patient will therefore be in the study between 3 days and 7 days. Study visits will last approximately 2 hours. We will aim to complete study write up within 12 months of the study ending. The study end date will be defined as the last study visit of the last participant recruited.

6.5 Withdrawal Criteria

Participants will be allowed to withdraw from the study at any point. We will not collect any further data from this participant however will use data available during their time in the study for the final study analysis. If it is in the participant's best interest the clinician in charge of the study may also choose to withdraw the participant. If participants lose capacity for any reason during that course of the study, they will be withdrawn.

7. Data Management and Statistical Analysis

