Figure 2. New LED experimental setup for our proposed laboratory-based study. Left: LED array (Hogga) to deliver red (660nm) and near-infrared (850nm) light – the same as utilised in our previous study. Right: LED device (Hogga) to deliver blue (415nm) light (very similar to our previous study – 405nm).

A custom-built configuration shall allow irradiation of the participants fingers/hands. The wavelengths shall be delivered sequentially to the patient's treated hand (i.e., red/infrared and then blue light). Similar to our previous study, we envisage that a future LTTT device would uniquely combine and deliver all three wavelengths simultaneously. However, for our planned experimental approach by using available LED-based light systems, this will enable us to achieve the intended aims of our study and is significantly less expensive than constructing a new custom-built treatment device.

Participation

Taking part is voluntary and it is up to patients to decide whether or not to take part. If they decide to take part, they are free to withdraw at any time without giving a reason. A decision to withdraw at any time will not affect their standard of any care they receive. If they do wish to withdraw, they simply need to inform a member of the research team and they will cancel any planned future visits. Any images and data collected up to the point of withdrawal will be retained by the research team for use in the study.

Participant will potentially be in the study for up to 7 days. If they lose capacity for any reason during that time they will be withdrawn from the study and no further study visits will take place. Any images or data collected before the participant in question lost capacity would be retained for use in the study analysis.

Study visit protocol

Participant progression throughout the study is presented in Figure 3. Study visits will be conducted in a temperature-controlled (at 23°C) laboratory at Salford Royal Hospital. Patients will attend a total of 3 study (morning) visits over 3 (ideally consecutive) days. The minimum time between study visits is 1 day, and the maximum time between study visits shall be 3 days. Patients can attend consecutive days because there is not expected to be any significant carry-over therapeutically relevant effect from the LLLT. Relevant patient-and disease-related demographics and characteristics shall be collected. At each study visit, any relevant change/s to current drug treatment will be documented.

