At each treatment study visit any safety issues (between visits) will be documented (e.g., new concerns about cutaneous changes). This will be documented on a separate safety CRF at visits 2 and 3 (attached with this application). Patient reported pain on a VAS scale (0-100, where 100 is the most severe pain imaginable by

the patient) directly attributed to the LLLT will be recorded immediately after treatment, on a separate tolerability CRF at visits 1, 2 and 3 (attached with this application), to assess tolerability, at each study visit.

Assessment of efficacy

Laser Doppler imaging (LDI); LDI which measures blood flow allows a perfusion map (in arbitrary units) to be produced of the studied area. We will perform LDI immediately before and after the light exposures and then every 10 minutes for 90 minutes. LDI will include all the digits (thumb and four fingers) and dorsum of both the *treated* and *untreated* hands. Bilateral (matching) standard regions of interest (ROI) shall be assessed on the treated and untreated hands all LDI time points. The rationale of imaging these sites is to demonstrate an objective *localised* increase in skin perfusion with light treatment, and whether this differs between the digits and dorsum of the hand.

Thermography: Thermographic assessment measures skin temperature and provides an indirect measure of small and large blood vessel function and can also be applied to SSc-DUs. Standardised thermographic images shall be acquired immediately before and after the light exposures, and then every 10 minutes for 90 minutes. As for LDI, thermography will simultaneously image the whole treated hand to capture the fingers and dorsal aspect, and with contralateral counterparts on the untreated hand.

Assessment of persistent cutaneous digital ischaemia

Taken from the hand original acquired LDI and thermography images (as above), for any digital (finger) ulcers (DU) or pitting scars (DPS) present, perfusion measurements will be assessed at the lesion center (DU/DPS 'core') and immediately adjacent tissue (DU/DPS 'periphery').

Assessment of digital skin fibrosis:

Rodnan skin score: By a trained assessor using the modified Rodnan skin score by manual palpation (0-3 score, where 0 is normal and 3 is severe skin fibrosis/sclerosis).

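### A delayed reaction that makes a participant withdraw after visit 1 or 2 has no stated route into the between-visit safety record

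*Protocol*

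**What the plan says.** Section 4 of the protocol puts safety and tolerability in the primary objective, alongside perfusion and temperature, across the light doses.

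Section 5, under 'Assessment of safety and tolerability', sets up two records:

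- Safety issues arising between visits: "This will be documented on a separate safety CRF at visits 2 and 3".
- Pain attributed to the light: a VAS taken straight after treatment at all three visits, on a separate tolerability form.

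Two places govern withdrawal:

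- Section 5, 'Participation': participants may leave without explanation ("they are free to withdraw at any time without giving a reason"). To do so, "they simply need to inform a member of the research team and they will cancel any planned future visits". What was gathered before that is kept: "Any images and data collected up to the point of withdrawal will be retained by the research team for use in the study".
- Section 6.5: "We will not collect any further data from this participant", followed by "however will use data available during their time in the study for the final study analysis". The next sentence adds that "the clinician in charge of the study may also choose to withdraw the participant" where this is in the participant's best interest. It gives no separate rule on data for that case.

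Section 7.1 limits the collection of addresses and telephone numbers to recruitment. Section 6.4 ends the study at the last participant's last visit and describes no later contact.

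**The concern.** The safety form looks backwards: what happened after one exposure is written down at the next visit. The withdrawal rule removes that next visit and stops data collection. A participant whose skin reacts at home after visit 1 or 2, and who decides for that reason not to return, leaves before the point at which the reaction would be recorded.

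This loss is informative, because the reaction itself causes the missing record. Those who do return are the ones well enough, or willing enough, to have another exposure. Since dose order is randomised, any of the three doses can be affected. The study is meant to refine the dose and to inform a later feasibility trial (sections 2 and 7.2), so an understated reaction count would be carried forward.

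The underlying difficulty is that the protocol treats stopping the light and stopping data collection as one event.

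**Working it through.** The protocol states no reaction rate, dropout rate or safety calculation, so there is no figure to reproduce. The check has two parts: tracing the record, then sizing the possible effect under stated assumptions.

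**Tracing the record**

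| Participant | Safety forms completed | Exposures with a later safety form |
|---|---|---|
| Completes all 3 visits | 2 (visits 2 and 3) | doses at visits 1 and 2 |
| Leaves between visits 1 and 2 | 0 | none |
| Leaves between visits 2 and 3 | 1 (visit 2) | dose at visit 1 only |

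In both withdrawal rows, the exposure that preceded leaving is the one without a form. What survives is the pain score taken straight after that exposure, plus the imaging up to 90 minutes afterwards. A reaction that appears later is in neither.

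**Denominator**

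- Exposures planned: 20 × 3 = 60.
- Safety forms planned: 20 × 2 = 40.
- Exposures with no later form even if everyone completes: 60 − 40 = 20, all of them at visit 3.
- Assumption: dose orders are balanced, so each dose falls at visit 3 for one third of participants. Participants per dose with a between-visit record: 20 × 2/3 = 13.3, or about 13.

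**Illustration (assumption: one reaction, followed by withdrawal before the next visit)**

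Exact one-sided 95% upper limits:

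- Zero events in n: upper limit = 1 − 0.05^(1/n). For n = 12: 1 − 0.05^(1/12) = 22.1%.
- One event in n: solve (1 − p)^n + n·p·(1 − p)^(n−1) = 0.05. For n = 13: p = 31.6%.

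| | Recorded | Upper limit |
|---|---|---|
| Under the present rule | 0/12 = 0% | 22.1% |
| With a form at withdrawal | 1/13 = 7.7% | 31.6% |

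**How likely is at least one such case?** With an assumed true risk p, among the 20 participants, of a reaction leading to withdrawal, the chance of at least one is 1 − (1 − p)^20. For p = 5% this is 1 − 0.95^20 = 64%. For p = 10% it is 1 − 0.90^20 = 88%. Both risks are assumptions; a lower risk gives a lower chance.

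**The case against.** The strongest reply is that the protocol loses less than it appears to.

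- **Earlier data are kept.** Both withdrawal passages say so, and pain is scored on the day of each exposure. A reader might infer that such a participant disappears from the whole safety and tolerability result. The text does not support that: immediate pain and the images already taken stay in. The loss is confined to the delayed reaction.
- **A reaction mentioned when withdrawing could count as known at that point.** Leaving involves telling a member of the team, and freedom to give no reason does not stop staff noting a reason that is offered. It would be too strong to say the protocol forbids such a note. It is silent, names no form for it, and its nearest instruction is to collect nothing more. That leaves the record to individual interpretation.
- **Withdrawal by the clinician.** A reader might take the no-further-data sentence to cover this case expressly. It precedes the clinician sentence and is not repeated, so that is one reading only. The clinician would also know the reason. Still, section 6.5 offers no other data rule, so the same loss may apply. The participant-initiated case does not depend on this.
- **Denominators.** A reader might compare rates out of all 20 participants per dose. That ignores the visit 3 exposures, which have no later form for anyone.
- **Few withdrawals are likely.** Participation lasts at most 7 days, and section 3 reports 46 exposures in the earlier study with no safety concerns. This bears on size, and section 5 identifies that dose as 10 J/cm², so it says nothing about 20 J/cm².
- **Unseen documents.** The safety form accompanied the application and may hold an unscheduled entry, and an analysis plan may set how withdrawals are reported. Neither can be checked here. An analysis plan cannot recover what was never collected.

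Section 8.4 halts the study if safety issues come to light. That shows the sponsor expects to notice them, but it supplies no means of recording them.

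**Conclusion.** The point stands in limited form. Under the rules as written, a delayed reaction after visit 1 or 2 that prompts withdrawal has no stated route into the between-visit safety record, and that record is therefore tilted towards safe on part of the primary objective. The direction follows from the text; the amount does not, because no reaction or withdrawal rate is given.

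With balanced orders and a single unrecorded reaction (both assumed), the reported figure for one dose would move from 7.7% to 0%, and the upper limit from about 32% to about 22%. In a study this small, one case is enough to change how a dose is described. The documents do not show that any bias will occur, only that nothing stated prevents it. This should be corrected, but it does not threaten the study.

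**What to change.** 1. In section 6.5 and under 'Participation', separate stopping the light from withdrawing consent to data collection.
2. At the withdrawal contact, whether started by the participant or the clinician, complete the existing safety form unless the participant declines. Record any skin change, its onset, the last dose received and the reason if offered.
3. Where a reaction is present and the participant agrees, record its outcome.
4. Amend section 7.1 so that telephone numbers may be used for this contact. At present their stated purpose is recruitment only, so a call would conflict with it.
5. Report withdrawals by last dose received alongside the safety results.

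This concerns data only. It leaves untouched when or why the light is stopped, and the participant may still refuse further contact. The cost is a wording amendment to the protocol and information sheet, a short call for the few who withdraw, and a safety result that may look slightly less favourable.

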7.1 Data Management

- All outcome measures will be recorded on standardised case report forms and safety/tolerability questionnaires.
- All participant data collection documentation including consent forms, will all be stored in a secure area and will never be taken off site.
- The following demographic data will be collected for the purpose of this study. Participant's address and telephone number will be collected for recruitment purposes only, in order to contact them, to inform them about the study and to see if they wish to take part.
 - o Gender
 - o Age
 - Hospital number
 - o Address
 - Telephone number
- Data will be transcribed from CRF / Questionnaires into excel spreadsheets / central database by members of the research team.
- The central electronic database will be pseudonymised, password protected and only accessible to certain members of the study team.

7.2 Statistical Analyses

To assess tolerability of irradiance wavelengths, VAS scores will be graphically explored. To observe the change over time, area under the curve will be calculated for each patient to estimate the blood flow/temperature, and a t-test will be used to test for differences. Our physiological study data shall inform the sample size calculation of a future feasibility RCT. However, in our previous investigation, which included eight patients (with 14 SSc-DU), we observed

an increase in perfusion of 15-32% post-irradiation with LTTT. We shall perform tentative analyses to explore the impact of our specified patient- and disease-related factors.

The study team including [name], [name], [name] and [name], will be responsible for transcribing, coding, de-identifying, storing/transferring, accessing and archiving study data.

8 Regulatory and Ethical Considerations

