Digital (finger) ulcers are common in patients with systemic sclerosis (SSc) otherwise known as scleroderma and many of the current treatments used can cause side effects or are not effective. We want to investigate a novel light-based therapy to potentially treat digital ischaemia (low blood flow) that causes digital ulcers.

In our previous study, our custom-built light-based treatment device, consisting of red, infrared, and violet wavelengths was found to be safe and feasible. There were also some early signals of potential benefit for digital ulcers in patients with SSc. To take this treatment approach forward, we now need to refine the optimal 'dose' of light.

Participants wishing to take part will need to attend Salford Royal Hospital for three study visits. At the first visit the research team we will examine the participant's fingers and back of their hands for any skin thickness changes (gently pinching the skin) as is routinely performed in the scleroderma outpatient clinic. Skin thickness will also be measured at these sites using an ultrasound machine.

At each visit, participants will receive one of three randomised 'doses' of the combination light therapy. The research team wishes to understand how the skin (blood flow and temperature) reacts to increasing dose of light. All patients will receive the three 'doses' of light over the three study visits (but not all in the same order), there is no placebo treatment. The light application to the skin will take approximately 15 minutes to complete.

We will measure the blood flow and temperature of the skin immediately before, directly after, and then every 10 minutes for 90 minutes after the light therapy. These will be measured using a type of scanner called 'laser Doppler imaging' and a thermal camera, which will each take approximately 1 minute (or less) per scan.

3 Background

Systemic sclerosis (SSc) is a complex autoimmune connective tissue disease characterised by microvascular abnormalities, fibrosis of the skin and internal organs, and immune system activation [1]. Digital ulcers (DUs) are common in patients with SSc and are responsible for much of the pain and disability associated with the disease [2,3].

SSc-Digital Ulcers (DUs)

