Light treatment within the red and near-infrared spectrum is believed to stimulate a wide number of cellular processes (often referred to as 'biostimulation') which are thought to benefit wound healing, including (but not limited to) stimulation of fibroblast and macrophage number and function, increasing leucocyte mobility, modulation of growth factors and inflammatory mediators, and by promoting collagen deposition and neovascularisation [25,26].

Infrared light is also associated with ambient heating and an increase in blood flow (although this is likely short-lived), and improved tissue oxygenation. Red light can also have an antimicrobial effect through excitation of naturally occurring porphyrins (30). In a blinded, randomised, placebo-controlled, single treatment trial, photodynamic therapy with red light and an exogenous photosensitiser caused a significant reduction in bacterial load of diabetic ulcers, and a trend toward ulcer healing [27].

Violet light also has an antibacterial effect including activity in vitro against Staphylococcus aureus [28]. Impact of the LLLT may occur both via effects on the ulcer bed and on the ulcer margins, including with respect to bacteria present. While blue light can reach bacteria residing on the surface or within the epidermis, bacteria can also colonize deeper dermal components of the skin, and blue light will be less effective than red/infrared in reaching these. DUs in patients with SSc are relatively superficial, with an average depth of 1 mm (as measured by high-frequency ultrasound); therefore, this is unlikely to be an important disadvantage [29]. While there is much less of a precedent for the use of violet (or blue) light to treat ulcers, it is important to consider that blue light is more photochemically active than red light and causes more reactive oxygen species generation [30]. Blue light has been shown to increase perfusion through stimulation of local nitric oxide (NO) release, with relaxation of vascular smooth muscle, and to increase wound healing in a skin excision model [31].

LLLT for SSc-DUs

We have previously developed at Salford Royal Hospital a custom-built LLLT device comprising infrared (850 nm), red (660 nm), and violet (405 nm) LEDs was utilized (Figure 1).

[figure not shown]

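### The efficacy AUC in Protocol 7.2 gives no role to the pre-light image or the untreated hand: lost precision for dose comparisons, and exposure to shared drift for the claim that light has an effect

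*Protocol*

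**What the plan says.** The efficacy analysis is one sentence in Protocol 7.2. Its purpose is given as "To observe the change over time". The summary is stated as "area under the curve will be calculated for each patient to estimate the blood flow/temperature", and the test as "a t-test will be used to test for differences". The sentence does not say whether the t-test compares doses, hands, or post-light with pre-light images.

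The data collection in 5 Study Design (Assessment of efficacy) is richer. For perfusion: "We will perform LDI immediately before and after the light exposures and then every 10 minutes for 90 minutes". On the control side: "Bilateral (matching) standard regions of interest (ROI) shall be assessed on the treated and untreated hands all LDI time points". Thermography likewise images the treated hand "with contralateral counterparts on the untreated hand". The reason given for imaging these sites is to show a localised rise in perfusion.

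Each patient receives 5, 10 and 20 J/cm² in randomised order, one dose per visit on different days. The Lay Summary states that "there is no placebo treatment". The dominant hand is treated unless there is a documented reason otherwise.

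**The concern.** The measure named in 7.2 does not match the aims it serves. An AUC of a level is neither a change over time nor a localised effect. The pre-light image would turn level into change, and the untreated hand would show whether a change is local. Both are collected at every visit and neither appears in the analysis sentence. The only earlier effect quoted in 7.2, a 15-32% rise after irradiation, is itself a change, so a level AUC cannot be set beside it.

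Two separate things are at stake:

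- **Comparing doses.** Each dose falls on a different day, so a level AUC carries whatever the hand's resting state was that day.
- **Claiming that light does anything.** There is no zero dose. If skin in both hands drifts during the visit, the treated hand alone cannot separate drift from light.

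The data are also meant to inform the sample size of a later RCT, so the variance and effect estimates will be used again.

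**Working it through.** The protocol gives no SD, alpha, power or sample size calculation, so there is no figure to reproduce.

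**Inputs from the protocol.** n = 20. Three visits, one dose each. Per visit: one pre-light image, one immediately after light, and nine at 10 to 90 minutes (11 in all), on both hands.

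**Assumed.** Two-sided alpha 0.05; the correlation r between a visit's pre-light value and its AUC, within patient across visits; equal variance of the two; and the size of any drift.

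**Step 1. What each summary contains.** For one visit write: treated hand before light = day + side; treated hand after = day + side + drift + light; untreated hand before = day; untreated hand after = day + drift.

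- Treated-hand level: day + side + drift + light.
- Treated-hand change from pre-light: drift + light.
- Treated minus untreated, after light only: side + light.
- Treated minus untreated, in change from pre-light: light.

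Only the last isolates a localised light effect. It also removes any standing difference between the dominant and the other hand.

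**Step 2. Dose comparisons.** Dose order is randomised within patient, so day and drift terms do not favour a dose and act as noise. Variance relative to the unadjusted AUC:

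- Pre-light value as covariate: 1 - r². At r = 0.5 this is 0.75 (25% cut); at r = 0.8 it is 0.36 (64% cut).
- Simple subtraction: 2(1 - r). At r = 0.5 this is 1.00 (no gain); at r = 0.8 it is 0.40.

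A paired t-test with n = 20 has 80% power at a standardised difference of 0.66. In units of the unadjusted SD of the dose difference, and ignoring the degree of freedom spent, the covariate brings this to 0.66 × √0.75 = 0.57 at r = 0.5 and 0.66 × √0.36 = 0.40 at r = 0.8.

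**Step 3. How far assumed SDs drive power.** A simulation took resting mean 100, a dose difference of 15, hand-specific day SD 8, image SD 8, and drift by 90 minutes of mean 20 and SD 10. With a day SD shared by both hands of 10, 20, 30 and 40, power for the treated-hand level was 90%, 52%, 29% and 20%. Pre-light subtraction gave about 99% throughout; subtracting the untreated hand, with or without the pre-light value, gave 96-97%.

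These inputs imply a high r. With day SD D, the covariance is D² + 64, the pre-light variance is D² + 64 + 64, and the AUC variance is about D² + 64 + 7 + 25 (averaged image error and drift). That gives r of about 164/√(228 × 196) = 0.78 at D = 10 and 1664/√(1728 × 1696) = 0.97 at D = 40. The large contrasts in power come from that end of the range. For dose contrasts, adding the untreated hand did not improve on the pre-light value: the SD of the dose difference was about 16.6 with both, against 13.6 with the pre-light value alone.

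**Step 4. The light effect.** Suppose no light effect and a linear drift reaching D₉₀ at 90 minutes in both hands. Its average over 0-90 minutes is D₉₀/2, so an assumed drift of 20% of the mean gives a false average rise of 10%, and 10% gives 5%. In simulation (day SD 25, other SDs as above, drift SD half its mean), treated-hand change from pre-light was significant in 99% and 67% of runs respectively. The treated-minus-untreated difference in change averaged 0 and was significant in about 5%.

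**The case against.** The strongest reply is that silence is being read as a decision. Section 7.2 never says the AUC is uncorrected. It introduces the AUC as a way to look at change, and leaves the contrast open. A treated-versus-untreated comparison would fit the stated interest in a localised effect and would cancel shared day and drift effects. Baseline handling and time window are often settled in a statistical analysis plan, which may exist here.

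Much of this stands. A reader might infer that the protocol has chosen to discard both controls; the text does not say so. What remains is that the protocol does state a summary, and the stated summary is of level. A hand-to-hand AUC comparison would still carry any standing side difference.

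A reader might also infer that day-to-day variation biases the dose comparison. It does not: in the simulations with no light effect, the dose comparison was significant in about 5% of runs for every summary.

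Nor do the documents support saying that most of the precision is lost. At r = 0.5 the standard error falls only by 1 - √0.75 = 13%, and with a day SD of 10% unadjusted power was already 90% under the assumptions shown.

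Drift is likewise a possibility, not a documented fact. The room is held at 23°C and no cooling challenge is described, although no acclimatisation period is stated either.

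Finally, a reader might infer that AUC windows differ by dose. That would need an AUC starting at the pre-light image and an exposure time that varies with dose; the protocol states only 10-15 minutes of light.

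**Conclusion.** The point holds as a free improvement, not as an error that invalidates the study. The stated AUC of level, with an unnamed contrast, leaves unused two controls that the protocol collects for the purpose it states.

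- **Dose comparisons:** precision is lost, without bias. By assumption, covariate adjustment cuts variance by 25% at r = 0.5 and by 64% at r = 0.8. The true r is unknown, and any specific power figure rests on SDs the protocol does not give.
- **Claim of a light effect:** a result from the treated hand alone would be biased by half of any linear drift common to both hands. With no placebo dose, only the untreated hand can remove this, on the assumption that the light does not alter the untreated hand. The size of such drift is not given.

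**What to change.** Amend 7.2, or fix it in the analysis plan before data are examined:

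1. For each patient, visit and hand, compute the time-averaged AUC over a fixed window of 0-90 minutes after light ends.
2. For dose comparisons, compare doses within patient with the same visit's pre-light value as a covariate, not by simple subtraction. This relies on the protocol's own assumption of no relevant carry-over between visits.
3. For the claim of a localised light effect, test the treated-minus-untreated difference in change from the pre-light image.
4. Name these contrasts in place of an unspecified t-test.

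Optionally, report the image taken immediately after light on its own, since the Background notes that "Infrared light is also associated with ambient heating and an increase in blood flow" and regards that increase as probably brief.

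The cost is wording only. Every image needed is already scheduled, with no extra visits, patients or measurements.
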